## 1 CLINICAL SIGNIFICANCE

Despite advances in the treatment of patients with heart failure (HF), there remains substantial residual morbidity and mortality. Even with insights into diverse mechanisms of myocardial dysfunction, virtually all current medical treatment is focused on modulating the "neurohormonal axis". Our project extends these principles to an emerging frontier, the ketone "metabolic axis", as a means of ameliorating symptoms through exogenous delivery of a ketone ester. In this pharmacokinetic study, we first seek to find the optimal dose of a ketone ester product. We will subsequently use this information to inform dosing for a randomized trial of ketone therapy in HF.

## 2 SPECIFIC AIMS

HF is a major public health problem: it affects 6.2 million people in the U.S. The lifetime risk for developing HF after the age of 40 years approaches 20%, and five-year survival after HF hospitalization is a dismal 35%. These statistics highlight the urgent need to identify novel therapies to reduce the substantial morbidity and mortality of the disease process. Current HF therapies focus on ameliorating pathophysiologic adaptations, including antagonism of the activated renin-angiotensin-aldosterone and sympathetic nervous systems, reducing excess vasoconstriction, and mitigating fluid retention. At its most basic level, however, HF is a metabolic imbalance - an inability of the heart to generate sufficient energy to adequately supply blood to the body, or only to do so at elevated filling pressures. The heart is a very metabolically demanding organ, which requires nearly 12 times its own body weight in ATP daily. Abnormal myocardial energetics have been described in both HFrEF. Targeting the metabolic axis in HF therefore may hold great therapeutic promise.

Under physiologic conditions, fatty acids are the predominant energetic substrate for the heart, providing 50-70% of the ATP need. Glucose serves as a secondary source, necessary for flexibility and adaptive fuel utilization shifts during embryologic development and during a diverse array of nutritional and physiologic conditions. However, two important studies lead by our team have demonstrated that free fatty acid oxidation is impaired in advanced HF due to mitochondrial substrate reprogramming, and the hypertrophied and failing heart utilizes ketone bodies as a metabolic substrate, in both animals and humans. It was previously unknown whether this shift was adaptive or maladaptive, but recent small and large animal data demonstrates that ketone body oxidation is an adaptive feature of the failing heart. Importantly, delivery of exogenous ketones improves pathologic cardiac remodeling and dysfunction while enhancing mitochondrial bioenergetics.

We now have a unique opportunity to study a ketone ester (KE), (R)-3-hydroxybutyl (R)-3-hydroxybutyrate (commercially known as "DeltaG"), that provides systemic ketosis in a deep phenotyping study of HF patients. Initial studies of DeltaG demonstrated significant improvement in exercise capacity among endurance athletes. In this first study, we attempt to find the optimal dose of the ketone product. As patients may be taking minimally ketogenic medications (SGLT2 inhibitors), we will study the pharmacokinetic effects of ketone ester with patients on, and not on, these medications.

Our Specific Aims are as follows:

Aim 1. To assess the pharmacokinetics and safety of ketone ester in patients on, and not on, SGLT2 inhibitors. We will perform serial peripheral blood sampling to understand the effects of acute ketone ester on pH, glucose, systolic blood pressure, and ketone levels to find an optimal dose of the product.

# Aim 2. To assess the effects of KE on metabolomics, proteomics, and systemic biomarkers (pending sufficient funding).

## **3 BACKGROUND AND SIGNIFICANCE**

HF affects 6.2 million Americans and is associated with substantial morbidity and mortality in the contemporary era. By 2030, the burden of HF is anticipated to surpass 8 million with an associated economic toll of a staggering \$69.8 billion. The cardinal clinical feature of patients with HF is reduced exercise capacity, which is associated with a substantial reduction in quality of life. Despite significant advancements in therapy for patients with HF, particularly among those with reduced ejection fraction (EF), many still suffer from limitations in exercise capacity and a poor prognosis. As such, exploring other avenues to reduce morbidity from HF is of vital interest from societal, economic, clinical, and patient-centered perspectives.

Recently, several alterations in the cardiac metabolism of patients with HF have been described, setting the stage for randomized trials of novel therapies that modulate energy fuel metabolism. Among healthy individuals, the heart, a very metabolically active organ, uses a combination of free fatty acids and glucose (to a lesser extent) as the primary sources of adenosine triphosphate (ATP) production. However, free fatty acid oxidation is impaired in the failing heart, and the heart increases its use of ketone bodies for fuel.

Ketone bodies (acetoacetate,  $\beta$ -hydroxybutyrate [BHB], and acetone) are water-soluble molecules produced from acetyl-CoA following breakdown of fatty acids (and amino acids) mainly in hepatic cells. Ketone bodies are typically absent from the circulation during the normal fed state, but are produced continuously during metabolic stress conditions and/or periods of carbohydrate deprivation such as acute medical stress, prolonged exercise, or starvation, and become a key source of energy to vital organs including the brain and heart under these circumstances. Ketone production has long been teleologically considered as a means to provide the brain with an efficient, alternative fuel source during starvation, sparing carbohydrate and protein stores, since the brain cannot effectively metabolize free fatty acids (which represent 99% of the body's energy stores). When completely oxidized in the citric acid cycle, ketones have a respiratory quotient similar to glucose (acetoacetate = 1.0, BHB = 0.89) and produce greater amounts of ATP, releasing approximately 30% more energy per molecule than pyruvate. The liver produces ketone bodies from mobilized fat stores that then can be utilized by neural tissue to produce ATP. It is therefore not surprising that several neurologic diseases have been treated, or are under study, with ketone therapy, such as epilepsy, Parkinson's disease, and Alzheimer's disease.

Macronutrient resources (low glucose, high free fatty acids) and hormonal signaling (low insulin, high glucagon, high cortisol) are the primary methods of regulating ketone production, and thus dietary modification has been studied extensively to treat these conditions (the "ketogenic diet"). Adherence to this diet, however, can be challenging, and may also be accompanied by dyslipidemia (due to increased flux of free fatty acids), impaired cardiac metabolism, or gastro-intestinal upset, leading to interest in alternative exogenous modes of delivery. Exogenous delivery of ketones holds several advantages over dietary modification such as increased compliance, lack of alteration on other fuel stores (such as intramuscular glycogen), and its unique effect of lowering both glucose and free fatty acids due to negative feedback on lipolysis.

Different formulations of oral ketone therapy have been studied, including ketone salts and KE. Oral ketone salts result in a high amount of salt intake (which may be problematic for patients with HF) and results in half the plasma concentration of D-betahydroxybutyrate (D-BHB). A novel KE compound, I-3-hydroxybutl(R)-3-hydroxybutyrate (DeltaG), has been extensively studied for the purposes of therapeutic exogenous ketosis and is approved as a nutraceutical by the Food and Drug Administration (FDA). Advantages of DeltaG consumption include a rapid rise of blood levels of BHB in humans to ~3 mmol/L within 60 minutes of consumption with moderate doses of KE, equivalent to a week of fasting, which is markedly increased from the levels of detectable ketones in normal populations (<0.5 mmol/L). By way of comparison, a carbohydrate-

restricted (high-fat) diet typically results in mild hyperketonemia, with BHB levels of  $\geq$  0.5 mmol/L, which is currently considered as an accepted definition of ketosis.

Benefits of KE therapy among athletes have already been demonstrated. In a blinded, crossover study of endurance athletes, DeltaG increased exercise distance by an average of 411 meters over 30 minutes cycling duration, demonstrating that ketone therapy improves exercise capacity among highly trained athletes. Importantly, it has been suggested that pathologic conditions that cause metabolic dysregulation, and where incremental improvements in energy transduction may translate to significant increases in exercise capacity, may afford the greatest clinical benefit, such as in HF.

Further data has emerged regarding potential benefits of intravenous infusions of sodium-3-hydroxybutyrate. In a crossover study of 16 patients with HF and reduced EF (HFrEF) randomized to 6 hours of ketone infusion vs. isotonic saline (placebo arm), infusion of the ketone increased cardiac output by 2 L/min with an absolute improvement in left ventricular EF of 8%. Notably, the hemodynamic effects of ketones were dose-dependent and detectable even in the physiological concentration range. While important, this trial was limited by use of an intravenous infusion (impractical for the outpatient management) and concerns related to salt infusion, such as pH disturbances and sodium loading. In addition, this trial did not assess patient-centered metrics, such as exercise capacity, which is an important determinant of quality of life in HF. However, the fact that intravenous ketone therapy increased cardiac output to this extent supports the hypothesis that there is a fundamental limitation of fuel utilization in HF that can be therapeutically targeted. In addition, recent data shows important improvements in cardiac output and function without significant safety concerns in patients with cardiogenic shock at 500 mg/kg of the KE.

In this first study, we seek to determine whether the optimal dose of a liquid ketone ester drink in patients on, and not on, SGLT2 inhibitors.

#### 4 Published Data on Ketone Ester

DeltaG is a ketone ester (KE) that undergoes complete enzymatic hydrolysis to form BHB (and R-1,3butanediol) by carboxylesterases expressed widely, including within the gastrointestinal tract, liver, and blood. R-1,3-butanediol, itself, is further metabolized in the liver by first-pass metabolism and blood to produce BHB by alcohol dehydrogenase and aldehydye dehydrogenase. BHB undergoes further metabolism to acetoacetate and acetone, though only BHB and acetoacetate are taken up by extra hepatic tissues as energy sources.

KE is eliminated through at least first order kinetics and capacity limited elimination. Elimination is accomplished via 3 predominant means, including (1) conversion to acetone and lung exhalation, (2) renal elimination (of BHB and acetoacetate, though this contribution is negligible particularly during exercise), and (3) uptake by tissues using monocarboxylate transporters for conversion to ATP.

Concentrations of the KE compound of roughly 3-5 mmol/L are reached within 60 minutes at doses comparable to what is studied here. The half-life of the compound is 0.8-3.1 hours. The KE compound has a very favorable safety profile with adverse effects limited to dose-dependent, gastrointestinal distress that typically occur only at the highest levels of administration (714 mg/kg).

Request for IND exemption: We believe this study qualifies under the criteria for IND exemption. DeltaG has been granted **GRAS** status through the FDA as a food, and the GRAS documentation will be separately submitted. We believe this study is exempt from the IND requirements because it meets the conditions of FDA guidance (sections VI.D.1 & VI.D.2). Specifically, DeltaG, as used in this study, is not intended for use "in the diagnosis, cure, mitigation, treatment, or prevention of disease". As DeltaG is only received on *one* study date as an acute study, and endpoints assessed here are for safety, we believe the use of DeltaG fulfills these critiera here. Participants will be notified in the ICF specifically that they will not benefit as a result of participating in the study. The intent of the study is to describe the acute effect of DeltaG (a food) on venous pH, glucose, and blood pressure as a safety mechanism. In addition, the results of this study are not intended to affect the marketing or labeling of DeltaG.

We have previously performed research with this compound at another institution in patients with heart failure, who have given IND exemption for the use of ketone ester. This letter has also been submitted.

## 5 Research Design and Methods

Overview: We first begin with a pharmacokinetic study to establish dosing among 20 HF participants.

## 5.1 Study population

#### Study population (Inclusion criteria)

Participants aged at least 18 years of age with a diagnosis of HFrEF and with systolic blood pressure ≥90 mmHg will be included for this study. We will recruit 20 HFrEF (LVEF <=45%) participants. Participants will be stratified by use of prescribed SGLT2i (taken as part of their clinical care and not provided through this research study). Participants will be recruited from within the Duke Health System.

## Exclusion Criteria

- Intentional ketogenic (high fat, low carbohydrate) diet (must be off ketogenic diet for 
  >7 days prior to visit)
- 2. Significant liver disease (cirrhosis) or alcohol abuse disorder (>14 drinks/week)
- 3. Unique cardiomyopathies: infiltrative/hypertrophic cardiomyopathy, pericardial disease, or other unique cardiomyopathies that in the opinion of the investigator would be less likely to respond to ketone therapy
- 4. Estimated glomerular filtration rate<25 mL/min/1.73 m^2 as the most recent value in the last year.
- 5. Type 1 diabetes mellitus
- 6. Use of ventricular assist device, history of heart transplant, or use of continuous inotropes
- 7. Pregnant women. Due to unknown affects of nutritional ketosis in pregnant women, pregnancy will be an exclusion. Accordingly, women of childbearing age with a menstrual cycle within the past year will be asked to submit a urine specimen for pregnancy testing.

## 5.2 Participant clinical data collection

We will assess the following clinical data parameters on study intake, which may include but are not limited to:

- 1. Age, date of birth, gender, race
- 2. New York Heart Association class
- 3. Smoking status, alcohol status.
- 4. Comorbidities (supplemented by chart view of the problem list): previous HF hospitalization in last 6 months, myocardial infarction, stroke, coronary artery bypass graft surgery, percutaneous coronary intervention, chronic obstructive pulmonary disorder, asthma, hypertension, peripheral artery disease,

atrial fibrillation or flutter, dyslipidemia, implanted cardioverter-defibrillator, pacemaker, and diabetes mellitus, and others.

- 5. Vital signs: height, weight, heart rate, systolic blood pressure, diastolic blood pressure, oxygen saturation, and others
- 6. Medications will be obtained from the medical chart and confirmed with the participant.

## 5.3 Pharmacokinetic study:

SGLT2i are standard-of-care ketogenic medications in HFrEF that minimally raise ketone levels though still well within normal limits (0.10mM to 0.13mM, normal <~0.5mM) through reducing insulin:glucagon ratio. Since exogenous ketones *increase* this ratio as shown in our previous work and *reduce* endogenous ketosis, the combination of exogenous ketones and SGLT2i is not expected to perpetuate ketoacidosis risk by SGLT2i (which has not been a significant concern in clinical trials of HFrEF). Further, recent work has supported the safety of ketogenic interventions in patients taking SGLT2 inhibitors. Additionally, pH changes with robust ketosis by KE are noted (1 study showed a pH decrease of 0.10 to an arterial pH of 7.31 after the ketone drink as an expected change). Nevertheless, we will first perform a dose-finding study in 10 HFrEF participants on SGLT2i and 10 not on SGLT2i to assess safety (Table 1). We will measure venous pH, glucose, blood pressure, and BHB every 60 minutes for 4 hours. After a standardized meal containing carbohydrate (to limit endogenous ketosis), we will assess 5 participants in each stratum using 250 mg/kg to initially target BHB levels ~1-2 mmol/L, and then dose escalate to 500 mg/kg for 5 participants which is predicted to achieve BHB levels ~3 mmol/L (safely achieved in HF patients previously with KE without inducing significant side effects including mild acidosis). This is also the dose used in a recent trial in cardiogenic shock without significant safety concerns but with significant efficacy. We will not escalate past 500 mg/kg given increasing risk for gastrointestinal symptoms.9, 37

Table 1. Pharmacokinetic Stud	y Details and Dose Escalation/De-escalation Plan

Strata	Dose	Timepoints assessed	Endpoints assessed
SGLT2i arm and no SGLT2i arm	250 mg/kg KE for 5 participants, then 500 mg/kg for 5 participants	Every 60 minutes for 4 hours	Venous pH, systolic blood pressure, glucose

Food may be provided to participants if they have hypoglycemia (glucose <55 mg/dl) but otherwise we will ask participants to refrain from consuming food after the ketone drink is administered until the 4 hour blood draw.

Prior to the ketone drink, we will collect blood –twice - in the fasted status (>8 hours of fasting) and then after a light breakfast. We will collect blood 6 times after ketone drink. There will be at most 8 blood draws as below.

Blood draw number	Approximate time of blood draw	Blood draw for endpoint assessment	Blood draw for storage
1	Fasting, prior to ketone drink		х
2	After light meal, prior to ketone drink		x
3	30 minutes after ketone drink		х
4	60 minutes after ketone drink	Х	x

5	90 minutes after ketone drink		х
6	120 minutes after ketone drink	X	x
7	180 minutes after ketone drink	x	x
8	240 minutes after ketone drink	x	x

Timepoints delinated here are approximate. We aim to draw blood as close to the timeline outlined here, but +/- 15 minutes from the timepoint is considered acceptable without deviation. Likewise, lack of blood draws at times not used for endpoint assessment will not be considered a deviation.

We preferentially enroll unique patients in this study (i.e. 20 different patients). However, in the event of difficult enrollment in the "no SGLT2i arm", participants currently taking an SGLT2i may enroll and hold the SGLT2i for at least 4 days (with the permission of their treating physician). This amount of time is similar to what is advised prior to some procedures (i.e. surgery). Therefore, participants could enroll twice in this study (in each arm).

A total of ~100 mL of blood will be obtained at this visit.

Blood samples will be stored (either within the Duke Heart Center or the Duke Molecular Physiology Institute) at -80C for later analysis. We may perform routine blood testing (metabolic panels, blood counts), comprehensive metabolomic/proteomic profiling from this peripheral blood, as well as other biomarkers, in addition to other testing, pending sufficient funding.

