## 7 Statistical analysis plan

Primary outcomes

- 1. Venous pH at 1 hour
- 2. Systolic blood pressure at 1 hour
- 3. Glucose at 1 hour
- 4. Beta-hydroxybutyrate level at 1 hour

Participant characteristics will first be summarized using means (standard deviations), medians (interquartile range), and counts (percentages) as appropriate for the type of variable and its distribution. We will plot summary estimates of venous pH, glucose, ketone levels, and systolic blood pressure over time, overall and stratified by SGLT2i use and ketone ester dose. We will compare whether achieved venous pH, glucose, ketone levels, and systolic blood pressure vary by background SGLT2i use, accounting for related baseline measurements. Sensitivity analysis will adjust for age, sex, ketone ester dose, eGFR, and hemoglobin a1c (if available). Repeated measures techniques (accounting for clustering at the level of the participants) may be used to assess overall changes in pH, ketone levels, systolic blood pressure, and glucose. We will describe peak ketone concentrations achieved by arm. Similarly, we will assess the relationship between peak ketone levels (dependent variable) and dose of KE (independent variable). P<0.05 will be used to indicate statistical significance.

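### Section 7 promises an SGLT2i comparison adjusted for baseline, but section 5.3 does not secure the pre-drink pH, glucose and BHB that it needs

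*Combined protocol and SAP*

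**What the plan says.** Section 5.3 and Table 1 set out two strata of 10 participants, on and not on an SGLT2 inhibitor. Each stratum receives "250 mg/kg KE for 5 participants, then 500 mg/kg for 5 participants".

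On measurement, section 5.3 says: "We will measure venous pH, glucose, blood pressure, and BHB every 60 minutes for 4 hours". The blood draw table that follows lists eight draws:

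- Draw 1 is fasting and draw 2 follows the light meal. Both come before the drink, and both are marked for storage only.
- The endpoint column is marked at 60, 120, 180 and 240 minutes after the drink and nowhere else.

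The text below the table adds that "lack of blood draws at times not used for endpoint assessment will not be considered a deviation". Stored blood is kept at -80C. A closing sentence lists tests that may be run on it, ending "in addition to other testing, pending sufficient funding".

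Section 7 names four primary outcomes at 1 hour: venous pH, systolic pressure, glucose and BHB. It commits to comparing whether achieved values "vary by background SGLT2i use, accounting for related baseline measurements". It also allows for repeated-measures methods to assess change in the same four variables. Section 5.2 lists systolic pressure among the vital signs gathered at intake.

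**The concern.** Section 7 states an analysis, and section 5.3 makes its input optional. A baseline-adjusted comparison of pH, glucose or BHB needs a pre-drink value for each participant. The only blood that could supply it is the blood that site staff may omit without recording a deviation, and that nobody is instructed to assay. Section 7 does not say which of the two pre-drink draws is the baseline. The choice matters most for glucose, because a carbohydrate meal falls between them.

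Two things are at stake. The first is whether a promised analysis can be done at all. Venous pH is the sharpest case. If it has to be measured on fresh blood, which is assumed here because the documents do not say, a value not taken on the day cannot be recovered from the freezer. Glucose and BHB might be recoverable. The second is precision: with 10 against 10, adjustment is one of the few ways to tighten the intervals without enrolling more people.

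**Working it through.** **Setting the text side by side**

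| Outcome | Pre-drink value needed by section 7 | What sections 5.2 and 5.3 secure |
|---|---|---|
| Venous pH | Yes | Draws 1 and 2 for storage only; may be missed; no assay committed |
| Glucose | Yes | Same |
| BHB | Yes | Same |
| Systolic pressure | Yes | A vital sign at intake, not timed to just before the drink |

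**The plan's own figure.** The sample size is a cell count: 2 strata × 2 doses × 5 = 20, which agrees with section 5.1. The documents give no power calculation, effect size or SD, so the results below are in units of the outcome SD.

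**Inputs.** There are 10 participants per stratum (section 5.3), and all 20 are assumed to be different people. Intervals are taken as two-sided 95%. The correlation between baseline and outcome is not in the documents, so a range is assumed. The outcome is taken as linear in baseline.

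**Unadjusted SGLT2i contrast (18 df).** The expected half-width is t × c × √(1/10 + 1/10), where c corrects for the sample SD averaging slightly below the true SD:

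2.101 × 0.986 × 0.447 = 0.93 SD.

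**Adjusted for baseline (17 df).** The expected half-width is about t × c × √[0.2 × (1 + 1/16)] × √(1 − r²). The 1/16 allows for chance baseline imbalance between the strata:

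2.110 × 0.985 × 0.461 × √(1 − r²) = 0.958 × √(1 − r²).

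| Assumed r | √(1 − r²) | Formula | Simulation (20,000 runs) |
|---|---|---|---|
| 0 | 1.000 | 0.958 | 0.958 |
| 0.3 | 0.954 | 0.914 | 0.916 |
| 0.5 | 0.866 | 0.830 | 0.828 |
| 0.7 | 0.714 | 0.684 | 0.683 |
| 0.8 | 0.600 | 0.575 | 0.574 |

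Adjustment starts to pay when 0.958 × √(1 − r²) falls below 0.927, which is at r of about 0.25. Below that it costs up to about 3% in width (0.958 / 0.927 = 1.033).

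**BHB.** Section 5.3 puts ketone levels at 0.10 to 0.13 mM before any exogenous ketone and expects 1 to 3 mmol/L after the drink. A starting value that small can explain little of the later spread, so the gain should be near the r = 0 row.

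**The case against.** The strongest reply is that section 7's promise presupposes that the baselines will be measured. Section 5.3 says blood will be collected twice before the drink, and the hourly measurement sentence can be read to include time zero. A column for endpoint assessment would naturally list only post-drink times. The funding caveat names panels, omics and other biomarkers, not pH or BHB. All of this is fair. The documents do not say that the baselines will go unmeasured. But the draw table is the operative schedule, it does not mark time zero, and the deviation rule excuses the omission. If staff would measure these values anyway, writing it down costs almost nothing.

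It is also fair that a few missed draws need not erase the gain. Take a model with dose, stratum and baseline, in which the two contrasts have the same half-width by the symmetry of the layout. With 3, 7 or 9 of 20 baselines missing at r = 0.5, 0.7 or 0.8, complete-case analysis gives 0.93, 0.95 or 0.93 SD, so nothing is gained over the unadjusted 0.93. Keeping all 20 and filling each missing baseline with the observed mean gives about 0.85, 0.80 or 0.79 SD, with coverage near 95%. The plan names neither method, and nothing in it suggests how many draws would be missed.

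A reader might infer three stronger points, which the documents do not support:

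- **Bias in the dose analysis.** Section 7 relates peak ketones to dose without naming stratum. Dose is balanced 5 against 5 within each stratum, so the omission does not bias the dose effect. Reading the 0.10 to 0.13 mM in section 5.3 as a shift of about 0.03 mM, and assuming an SD of 0.5 mM, the half-width is 0.470 mM without stratum and 0.472 mM with it.
- **Lost precision in dose contrasts for pH, glucose or systolic pressure.** Section 7 plots these by dose but states no dose test for them, so there is no stated analysis to weaken.
- **A pH decision rule that cannot be applied.** Section 5.3 notes that "1 study showed a pH decrease of 0.10 to an arterial pH of 7.31 after the ketone drink as an expected change". That is background from one cited study, not a threshold for this trial. The primary outcome is the venous pH level at 1 hour, which can be computed without a baseline.

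**Conclusion.** The point holds for pH, glucose and BHB, and its severity is minor. A stated analysis depends on values that the stated schedule does not secure. The primary outcomes themselves remain computable, and the dose escalation is not in question.

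The size is the gap between the unadjusted and adjusted SGLT2i contrasts: 0.93 SD against 0.83, 0.68 or 0.57 SD at correlations of 0.5, 0.7 or 0.8, with a small loss if baseline carries no information. These figures rest on the assumed correlations, a linear baseline relation and 20 different people. Section 5.3 allows someone to enrol once in each arm if recruitment is hard; the contrast would then be partly paired and the figures would change. That the loss of pH would be permanent rests on the assumption about frozen samples. For BHB the issue is the feasibility of the promised analysis and hardly its precision. Systolic pressure needs no blood draw and lacks only a reading timed to just before the drink.

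**What to change.** 1. In the section 5.3 draw table, mark draw 2 (after the meal, before the drink) for endpoint assessment of venous pH, glucose and BHB.
2. Record systolic pressure at the same time.
3. In section 7, name draw 2 and that reading as the baseline for the SGLT2i comparison and for any analysis of change.

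Draw 2 is the better choice because it follows the meal and so reflects the state in which the drink is taken.

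The cost is three assays on a draw already planned, at up to 20 visits (3 × 20 = 60 measurements), plus one blood pressure reading per visit and a sentence in section 7. No participant, visit or draw is added. A missed draw 2 would become a deviation.

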## 6 Risks and Safety Assessment

Ketone Ester: This proposal includes a ketone ester which is commercially available and has been granted "Generally Regarded as Safe" (GRAS) status from the FDA. This KE undergoes complete enzymatic hydrolysis to form BHB (and R-1,3-butanediol) by carboxylesterases expressed widely, including the gastrointestinal tract, liver and blood. R-1,3-butanediol, itself, is further metabolized in the liver and blood to produce BHB. The TMax ranges from ~1-3 hours. Elimination is accomplished via conversion to acetone and lung exhalation, renal elimination, and uptake by tissues using for conversion to ATP (including the brain, heart, kidney, and skeletal muscles). We exclude participants both with a history of significant renal impairment (eGFR <25 ml/min/m^2) or hepatic impairment (history of cirrhosis, alcohol abuse). Peak concentrations of KE are reached around 60 minutes at doses anticipated to be administered here. The half-life of BHB from the compound is 0.8-3.1 hours. Adverse effects are infrequent and dose-dependent; gastrointestinal distress occurs at the highest levels of administration (714 mg/kg), consistent with our own experience. No clinically significant changes in vital signs, lipid levels, blood counts, renal function, and urinalysis parameters were observed at doses similar to those studied here. Participants may be on SGLT2i which are minimally ketogenic medications in themselves with minimal risk for ketoacidosis in HF. As outlined in this section, it is not anticipated that the KE will amplify risk of ketoacidosis with SGLT2i given the differing biologies of endogenous versus exogenous ketosis. However, this potential risk will be outlined to participants who enroll in this study. **Dose:** In this proposal, we will perform a pharmacokinetic study to determine optimal dose without significant safety concerns which will be explored in our pharmacokinetic study. Our product is purchased commercially as "DeltaG" (TdeltaS, Orlando, FL). We have administered these doses proposed here to 15 HFpEF patients in an ongoing study without significant adverse events related to the nutraceutical. We will monitor for any adverse events throughout the study visit. The compound half-life is short as indicated above. To aid intolerability, participants are served a light meal. In addition, water (which may be naturally flavored and/or carbonated) is freely permitted.

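### Under the fallback for filling the no-SGLT2i arm, participants may hold a standard-of-care SGLT2i for at least 4 days, yet the protocol text states adverse event monitoring only for the study visit

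*Combined protocol and SAP*

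**What the plan says.** The plan wants 10 HFrEF participants on an SGLT2i and 10 not on one, and it prefers 20 different people. Section 5.3 adds a fallback for slow recruitment to the second group: "participants currently taking an SGLT2i may enroll and hold the SGLT2i for at least 4 days (with the permission of their treating physician"). The length is justified by analogy: "This amount of time is similar to what is advised prior to some procedures (i.e. surgery"). One consequence is stated: "Therefore, participants could enroll twice in this study (in each arm").

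The drug belongs to the participant's ordinary treatment. Section 5.1 describes it as "taken as part of their clinical care and not provided through this research study", and Section 5.3 says that "SGLT2i are standard-of-care ketogenic medications in HFrEF".

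On safety follow-up, Section 6 states: "We will monitor for any adverse events throughout the study visit". The pH, glucose, blood pressure and BHB measurements also belong to that visit and end 4 hours after the drink. Section 6 discusses ketoacidosis in people who are on an SGLT2i and says: "However, this potential risk will be outlined to participants who enroll in this study". It does not discuss stopping the drug.

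**The concern.** The monitoring window suits the ketone ester, which is given once and has a stated half-life of 0.8 to 3.1 hours. It does not suit the hold. The hold is a change in treatment made because of the study, it lasts days, and it begins before the monitoring window opens and may continue after it closes.

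What is at stake is the safety of the participants who use the fallback. Someone might have an event while off the drug on day 3, or might not restart after the visit. The protocol text has no step aimed at learning of either. The documents describe no benefit to the participant from the interruption; it serves enrolment.

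**Working it through.** No formula in the plan bears on this point and there is no stated figure to reproduce. The check sets the stages of a fallback participant's time off drug beside what the protocol text provides for each.

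1. **First withheld dose to the visit (at least 4 days; no maximum stated).** No event collection is stated for this stage. Section 5.2 records heart failure hospitalization over the preceding 6 months, vital signs, and medications checked with the participant, all at study intake. If intake falls on the visit day, some events during the hold could surface there. If intake comes before the hold, they could not. The timing is not stated.
2. **The visit.** Section 6 provides adverse event monitoring, and Section 5.3 provides hourly safety measurements for 4 hours after the drink. This stage is covered.
3. **Visit to restart (length not stated).** There is no restart instruction, no contact after the visit and no event collection. A participant who enrols in both arms might be seen again at the on-SGLT2i visit, but the order of the two visits is not given and a second enrolment is not required.
4. **Visit cancelled after the hold has begun.** Nothing is stated.

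Sections 1 to 7 were read for any restart step, maximum hold, contact after the visit or check during the hold, and none was found. Section 7 lists four primary outcomes, all at 1 hour, and no adverse event summary, so it does not fill the gap.

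**Reach.** The no-SGLT2i arm has 10 places (5 at each dose). The fallback may fill none or all of them, so it applies to 0 to 10 of 20 enrolments.

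**Cost of the follow-up contact.** 1 contact × 0 to 10 fallback participants = 0 to 10 contacts.

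**The case against.** The case for leaving the text alone has weight. The hold is a contingency that may never be used. The treating physician must agree to it, and because that physician's patient takes the drug as clinical care, restarting it would naturally fall to the same clinic. The word hold itself implies resumption. An instruction to resume is the kind of thing found in consent or participant material, which was not available here and cannot be counted as missing.

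Most of this stands, and it limits the point. The lack of a written restart instruction would not be enough by itself. What remains is narrower. The physician's agreement covers the start of the hold, but no one is assigned to confirm that it ended, and nothing makes an event during it reach the study. The comparison with surgery supports the duration only.

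A reader might infer that events during the hold would certainly be missed. The documents do not support that, because intake questions or recall at the visit could reveal them. A reader might also compare the hours of the visit with the days of the hold and treat the ratio as a measure of risk. It would measure clock time only: events can be recalled at the visit, and the documents give no event rate.

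**Conclusion.** The concern holds in a limited form. A study-prompted interruption of standard-of-care treatment lies largely outside the only adverse event window that the protocol text states. Events before the visit may surface, but not through any systematic step, and the time from visit to restart is not covered. This is an inexpensive safety improvement for 0 to 10 enrolments and not a flaw in the trial's inference.

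A reader might go further and infer that residual SGLT2i effect after a short hold would distort the comparison between arms. The documents do not establish this. Section 5.3 says that these drugs "minimally raise ketone levels though still well within normal limits (0.10mM to 0.13mM, normal <~0.5mM"), but those are cited summary values. Their difference neither shows carry-over nor sets an upper limit for an individual, and Section 7 already accounts for baseline measurements. No effect on primary outcomes, sample size or alpha is claimed.

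The conclusion assumes that the protocol text is the governing statement of adverse event collection, and that consent pages or case report forms, if they cover restart, do not also extend event recording to the hold.

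**What to change.** For fallback participants only:

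- At the visit, ask about and record adverse events since the first withheld dose.
- When the visit ends, or if it is cancelled, tell the participant to resume the SGLT2i unless the treating physician advises otherwise.
- Make one short follow-up contact to confirm restart and record any event since the visit. Day 7 is an example. The documents give no figure, and any time from 3 to 14 days would be workable. After a cancelled visit, the same contact should cover the time since the first withheld dose.
- Report these events separately from events after the drink.

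The cost is a short amendment and one contact per fallback participant: 0 to 10 in total, assuming that no cancelled visit is replaced by a new participant. If the fallback is never used, no contacts are needed. No limit on enrolment is added.
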